# Implementation of Antimicrobial Stewardship Directed PCT Testing and Treatment Algorithm

The antimicrobial stewardship team currently performs daily prospective audit and feedback for all patients admitted to VCH who receive antibiotics, providing in-person recommendations regarding antimicrobial modifications to providers as needed. This will continue in the standard of care arm. Current standard of care includes obtaining blood cultures, with or without CRP or other laboratory studies, and administering one or more broad spectrum antibiotics such as cefepime, piperacillin-tazobactam, and vancomycin for a minimum of 48 hours.

Prior to study initiation, the antimicrobial stewardship team will perform targeted education to ICU providers (attending physicians, residents and nurse practitioners) on the benefits and limitations of PCT use. A PCT-based algorithm to guide clinician decisions about antibiotic escalation or de-escalation will be disseminated to ICU providers (Fig. 1), displayed in ICU workrooms, and available on the intranet. PCT levels will be measured daily for the initial 3 days following randomization and then at day 5 post-randomization. Subjects in the intervention group will have a stewardship provider ([name]) review their records daily and make in person rounds in the ICU to strongly encourage provider adherence to the PCT testing and algorithm-based management. De-escalation of antibiotics will be recommended if the PCT level falls by 80% or more of the peak PCT level, or when the PCT level is less than or equal to 0.25  $\mu$ g/L (Fig. 1). Continuation or escalation of antibiotics will be recommended if PCT level is greater than or equal to 0.5  $\mu$ g/L, or increased as compared to previous peak PCT level. These levels are comparable to those used in previously cited studies.

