#### **Laboratory Analysis**

The Roche Procalcitonin test is a diagnostic test that is FDA approved for use in adults and has been approved by the VUMC laboratory formulary committee. It will be available for routine clinical use across the medical center, including in children at VCH in the near future. Although the Roche PCT test is not approved for use in children, the same test manufactured by Biomerieux does not have an age restriction on its FDA approval. This study is not intended to support approval of the test in children, nor promote non-approved indications. In this study we will use the Roche PCT test in an off-label population (children), but it will be used within the scope of clinical practice at Vanderbilt, following VUMC-approved guidance. A group of ICU, ED, and ID physicians and the chemistry lab director were involved in developing the strategy for reporting PCT results in the VUMC electronic medical record. The planned test reporting comments and PCT threshold interpretations are more conservative than used in some studies (Fig. 1) and are shown below:

Procalcitonin can help differentiate viral from bacterial respiratory infection. Procalcitonin may be used to guide antibiotic de-escalation in sepsis (when compared to admission level):

PCT < 0.1 ng/ml Bacterial infection very unlikely

PCT 0.1 to 0.25 ng/ml Bacterial infection unlikely

PCT 0.25 to 0.5 ng/ml Bacterial infection possible

PCT > 0.5 ng/ml Increased probability of bacterial infection, encourage antibiotic therapy

Serum PCT levels will be determined daily per VCH Laboratory protocol, using the Elecsys BRAHMS PCT test. The required blood volume is 0.5 - 1 mL and the estimated turnaround-time for the test is 3 hours or less. We will apply for a waiver of consent for the first blood sample, so that patients admitted to the ICU who are started on IV antibiotics will have leftover blood that is obtained during routine clinical care stored in a study refrigerator until study consent is obtained. For subjects enrolled in the intervention arm, PCT levels will be monitored at study enrollment, every 24 hours for the initial 2 days following randomization, and then at day 5 post-randomization. Whenever possible, leftover serum, from clinically collected specimens, will be used for PCT testing. For subjects in both arms, CRP, white blood cell count, and other relevant laboratory tests that are obtained for routine clinical care will be abstracted from the medical record.

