#### **Study Outcomes**

The **primary outcome** is days of antibiotic therapy in the first 14 days following randomization. **Secondary outcomes** are duration of broad-spectrum antibiotic therapy (defined as vancomycin, daptomycin, amikacin, ceftazidime, cefepime, piperacillin/tazobactam, aztreonam, carbapenems), time from randomization to first appropriate antibiotic modification (escalation or de-escalation), 30-day mortality, reinitiation of antibiotics for a bacterial infection within 30-days of antibiotic discontinuation, length of ICU stay, length of overall hospital stay, ventilator days, rates of antibiotic-

associated complications (i.e. rash, neutropenia, thrombocytopenia, acute kidney injury [defined as increase in serum creatinine  $\geq 0.3$  mg per dL or  $\geq 1.5$ -fold from baseline, or urine output < 0.5 mL per kg per hour for more than six hours], hepatotoxicity [defined as > 2-fold increase in alanine aminotransferase, ALT, or conjugated bilirubin], or *C. difficile* infection), infection with multi-drug resistant organisms (defined as methicillin-resistant *S. aureus*, vancomycin-resistant *Enterococcus*, 3rd generation cephalosporin non-susceptible *Enterobacteriaceae*, multi-drug resistant *Pseudomonas aeruginosa* [resistant to aminoglycosides, cephalosporins, floroquinolones and carbepenems], carbepenem-resistant *Acinetobacter*, and *Candida* spp obtained from otherwise sterile sites [i.e. blood or urine cultures]), cost of antibiotics from hospital billing data, and adherence to the PCT-guided algorithm.

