### 7.0 Risks

Risks include those associated with routine blood draws – pain, redness, soreness, bruising, or infection may occur at the needle stick site. Rarely some people faint. We plan to offer EMLA cream to subjects prior to blood draws. A maximum of 4 blood draws will be obtained for procalcitonin testing in patients randomized to the intervention arm. Whenever possible, for PCT testing, we will use leftover blood from routine laboratory testing performed as part of ICU care.

Because PCT has not been well studied for making antibiotic modification decisions in children, there may be the risk of premature cessation of antibiotics. However, to prevent this from happening, all decisions to stop or continue antibiotic therapy will be made by the ICU attending physician, based on clinical judgement and standard of care studies such as bacterial cultures, WBC,CRP, and radiographic evaluations

The decision to start antibiotic treatment will in no way be affected by the study. In all subjects antibiotics will be started based on clinical suspicion of infection or microbiologic evidence of infection. This decision is at the discretion of the treating intensive care physician. Similarly, the decision to obtain PCT testing and/or adhere to the PCT algorithm or stewardship recommendations will be at the discretion of the ICU attending physician.

All subjects in both arms will have baseline audit of antimicrobial orders with feedback to providers by the antimicrobial stewardship team. For subjects in the intervention arm, the stewardship team will additionally recommend PCT testing and treatment, with recommendations to initiate or expand antibiotic use at PCT levels > 0.5 ug/L and to stop antibiotics when PCT levels decrease by >80% from peak concentration or to an absolute value < 0.25 ug/L.

Multiple studies to date have demonstrated that procalcitonin-guided antibiotic de-escalation algorithms are as safe as standard of care management in the adult ICU setting. As such, we do not anticipate increased risk of infection relapse rates or

increase in 30-day mortality between groups. These parameters will be monitored throughout the study and adverse events will be recorded and reported as detailed below.

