Table summaries will present the following study population characteristics by randomized arm. All variables, as noted below, will be analyzed on the continuous scale or as categories or both as appropriate.

For continuous variables, summary statistics will include # of participants and median (Q1-Q3).

For categorical variables, summary statistics will include number (%) for each category. In calculation of percentages, participants with missing data will not be included in the denominator.

We will calculate the median days of antibiotic therapy per patient within the first 14-days post randomization in both treatment arms, together with the interquartile range. The primary test will be a Wilcoxon rank-sum test without the assumption of normality.

We will compare other continuous outcomes using a Wilcoxon rank-sum test, and categorical outcomes using a Pearson's chi-squared test.

We will perform a post-hoc analysis using a multivariable ordinal logistic regression model to assess the association between randomization group and the overall antibiotic duration of therapy per patient, adjusting for sex, recent surgical procedure, antibiotic indication of possible sepsis, and fever, vasopressor support and need for mechanical ventilation at enrollment.

We will perform a Cox proportional odds model adjusting for location of enrollment and study day to evaluate the hazard ratio for time to cessation of antibiotics within 4-days and within 10-days.

Final Analysis Considerations

The primary analysis will be a modified intention to treat (ITT) analysis. Participants who died prior to randomization, underwent bone marrow transplant or solid organ transplant prior to or after randomization, who are diagnosed with cystic fibrosis, or who ultimately are diagnosed with endocarditis, osteomyelitis, meningitis, mediastinitis or other invasive infection for which long duration of antibiotics is needed will be considered unevaluable. These are all issues that would otherwise qualify as exclusion criteria at the time of enrollment.

1. Study Population

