1.2 Study Population Characteristics

Table: Demographics

- a. Current age on day of study entry (in years): Continuous
- b. Sex at birth: By category (male/female)
- c. Self-reported race, ethnicity and race/ethnicity as defined by NIH reporting standards: By category

2. Health Characteristics/Status at Entry

- a. In pediatric ICU or pediatric cardiac ICU at randomization
- b. Requirement for intravenous vasopressor agents (categorical, yes or no)
- c. Mechanical ventilation (categorical, yes or no)
- Fever (temperature >38.0 deg F) or hypothermia (temperature <35.0 deg F) (categorical, yes or no)
- e. Surgical procedure within 2 weeks prior to enrollment (categorical, yes or no)
- f. Presence of comorbidity
 - Heart disease
 - Gastrointestinal disease
 - Neurologic disease
 - Bone/joint infection
 - Renal disease
 - Hematologic disease
 - Oncologic disease
 - Pulmonary disease
 - Other
 - No comorbidities
- g. Indication for antibiotics
 - Concern for sepsis
 - Pneumonia
 - Meningitis/encephalitis
 - Urinary tract infection
 - Other
- h. Attending physician on the day of enrollment

• Choose 1 of 20 pediatric ICU attending physicians who wrote the progress note for the patient on the day of enrollment

3. Antibiotic Use

Table: Days of antibiotic therapy per patient within 14 days (PRIMARY OUTCOME). Patients who are continued on antibiotics longer than 14 days will be assigned a time of 14 days per antibiotic.

Table: Days of broad-spectrum antibiotic therapy per patient within 14 days. Patients who are continued on broad-spectrum antibiotics longer than 14 days will be assigned a time of 14 days per antibiotic.

Table: Count (%) of patients on any antibiotic longer than 72 hours

Table: Count (%) of patients on broad-spectrum antibiotics longer than 72 hours

Table: Count (%) of patients on IV antibiotics longer than 72 hours

Table: Count (%) of patients on 2 or more antibiotics at 24, 48, 72, and 96 hours after enrollment

Table: Days of IV antibiotic therapy per patient within 14 days. Patients who are continued on IV antibiotics longer than 14 days will be assigned a time of 14 days per antibiotic.

Figure: Time to first antibiotic modification, using the empirical cumulative distribution function.

Figure: Percent of patients on antibiotics within 14 days of enrollment, using a Cox proportional hazards model

4. Sensitivity and Additional Analyses of the Primary Endpoint

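### A Cox cessation curve cannot show the percent of children on antibiotics once some restart, and the supporting cessation model is misnamed and uses nested windows

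*SAP*

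**What the plan says.** Two places in the SAP deal with when antibiotics stop.

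- SAP, 3. Antibiotic Use: "Figure: Percent of patients on antibiotics within 14 days of enrollment, using a Cox proportional hazards model". The event, the covariates and any stratification by arm are not given.
- SAP, F. Analysis Plan, Statistical Considerations: "We will perform a Cox proportional odds model adjusting for location of enrollment and study day to evaluate the hazard ratio", the outcome being "time to cessation of antibiotics within 4-days and within 10-days".

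The SAP does not say whether cessation means the first or the final stop. It gives no rule for restarts, death or discharge in these analyses, and no check of proportional hazards.

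The protocol (6.0, Study Outcomes) lists as a secondary outcome "reinitiation of antibiotics for a bacterial infection" within 30 days of stopping. Neither the SAP's outcome list nor its planned tables include it.

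The protocol describes the PCT schedule twice. Under Implementation: "PCT levels will be measured daily for the initial 3 days following randomization and then at day 5 post-randomization". Under Laboratory Analysis: "PCT levels will be monitored at study enrollment, every 24 hours for the initial 2 days following randomization, and then at day 5 post-randomization". Both end at day 5, and section 7.0 adds: "A maximum of 4 blood draws will be obtained for procalcitonin testing".

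The primary analysis is separate: a Wilcoxon rank-sum test on days of therapy within 14 days.

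**The concern.** The figure's label and its method refer to different quantities. The percent on antibiotics on a given day can rise when children restart. A curve from a model with one terminal event per child cannot rise. If the event is the first stop, a child who restarts is shown as off treatment. If it is the final stop, antibiotic-free gaps are shown as on treatment. Neither version gives the labelled quantity. The protocol names premature cessation as a risk, and the SAP has no reinitiation table, so this figure is a natural place for a reader to look for restarts.

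The second issue is the shape of the effect. With arm as a covariate, one hazard ratio governs the separation of the curves all the way to day 14. If the effect weakens after the last scheduled test, the fitted curves will be too close early and too far apart late.

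The third is the text model. Proportional odds and proportional hazards are different models, and a proportional odds model does not yield a hazard ratio. The 0-4 day window also lies inside the 0-10 day window, so the two hazard ratios are not separate pieces of evidence about early and late effects.

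**Working it through.** The documents give no hazard ratio, event count or restart rate for these analyses, so there is no planned figure to reproduce. The numbers below are illustrations under stated assumptions.

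**Inputs**

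- Control: exponential stopping with mean 4 days, hazard 1/4 = 0.25 per day. The 4 days is the average course in protocol 10.0; the exponential form is assumed.
- PCT arm to day 5: hazard ratio 4/2 = 2 (hazard 0.50). This follows from the 4-day average and the 2-day difference in protocol 10.0 under exponential stopping.
- PCT arm after day 5: hazard ratio h = 1.0 (effect ends) or 0.6 (partial reversal). Both are assumed.

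**Non-proportional hazards**

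True proportions not yet stopped:

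- Control: S_C(t) = exp(−0.25t)
- PCT: S_P(t) = exp(−0.5t) to day 5, then exp(−2.5 − 0.25h(t − 5))

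Day 5: exp(−1.25) − exp(−2.5) = 28.7% − 8.2% = 20.4 points.

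Day 14, h = 1.0: exp(−3.5) − exp(−4.75) = 3.02% − 0.87% = 2.2 points.

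Day 14, h = 0.6: exp(−3.5) − exp(−3.85) = 3.02% − 2.13% = 0.9 points.

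The large-sample Cox hazard ratio for each window solves the partial-likelihood score equation with arm as the only covariate. The arm curves then come from the Breslow baseline of the 14-day fit.

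| After day 5 | Cox HR, 0-4 / 0-10 / 0-14 days | Day-5 gap, Cox vs true | Day-14 gap, Cox vs true |
|---|---|---|---|
| h = 1.0 | 2.00 / 1.84 / 1.81 | 17.6 vs 20.4 | 3.7 vs 2.2 |
| h = 0.6 | 2.00 / 1.76 / 1.69 | 15.7 vs 20.4 | 4.4 vs 0.9 |

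The 10-day hazard ratio stays at 1.76 to 1.84 although the assumed ratio after day 5 is 1.0 or below.

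**Overlap of the windows**

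Share of 10-day cessations already reached by day 4 (h = 1.0):

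- Control: (1 − e^−1)/(1 − e^−2.5) = 0.632/0.918 = 69%
- PCT: (1 − e^−2)/(1 − e^−3.75) = 0.865/0.976 = 89%

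With a control median of 4 days and an early hazard ratio of 1.5 falling to 1.0, the shares are 61% and 73%.

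**Restarts**

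Assume 10% of those who stop restart 2 days later for 5 days. On day d a child is on the second course if the first stop fell between d − 7 and d − 2. The first-stop curve therefore understates use by 0.10 × [S(d − 7) − S(d − 2)].

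- Day 7, PCT: 0.10 × (1 − e^−2.5) = 9.2 points. This is the peak.
- PCT at days 8, 10 and 14 (h = 1.0): 5.4, 1.8 and 0.4 points.
- Day 7, control, same 10%: 0.10 × (1 − e^−1.25) = 7.1 points.
- Shift in the day-7 gap with equal rates: 9.2 − 7.1 = about 2 points.
- Day 10: control 3.4, PCT 1.8, so the direction reverses.

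A less aligned set of assumptions was also run: control median 4 days, hazard ratio 1.5 to day 5 then 1.0, restart 1 to 4 days after stopping, second course of median 4 days. With 10% restarting in both arms, the day-7 gap displayed is 10.6 points against a true 9.7. With 5% in control and 15% in the PCT arm, it is 10.3 against 5.5.

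**The case against.** The best defence is that nothing decisive rests on this. The primary test is a rank-sum test on 14-day days of therapy, and that count can include days after a restart. The SAP also tabulates antibiotic use beyond 72 hours, and use of two or more antibiotics at fixed times, without a Cox model. This stands, and it is why the point is minor.

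Four stronger readings might be inferred, and the documents do not support them.

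- *The plan ignores restarts.* The SAP is silent on first or final stop; it does not state that restarts are disregarded. What can be said is that it has no rule for them and that the chosen curve cannot display them.
- *The effect cannot be constant.* The end of testing at day 5 makes a changing effect plausible, not certain. Earlier results may keep influencing decisions, and daily stewardship review has no stated stop.
- *The figure forces proportionality.* Curves stratified by arm are not excluded and would avoid it, though they still could not show restarts. Reporting 4- and 10-day ratios also gives some view of attenuation.
- *The figure hides relapse in the PCT arm.* The comparison is materially misleading only if restart rates differ by arm. Nothing in the documents says they will, and protocol 7.0 anticipates no increase in relapse.

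The effects are also modest at this sample size. The day-14 excess is 3.7 − 2.15 = 1.55 points or 4.44 − 0.89 = 3.55 points, about 2 to 5 children in an arm of 140 (half of the SAP's 280). If all 280 children stop, the standard error of the log hazard ratio is about √(4/280) = 0.12. The log of 2.00/1.84 is 0.08, so the two ratios would be hard to tell apart.

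**Conclusion.** The concern holds as a minor point. Three parts rest on the text alone: the figure's method cannot deliver its labelled quantity once a child restarts, the model name contradicts the estimate it is to produce, and the two windows are nested.

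The sizes rest on assumptions. If arm is a covariate and the effect fades after day 5, the Cox curves understate the day-5 gap by about 3 to 5 points and overstate the day-14 gap by about 1.6 to 3.6 points. A true day-14 gap remains in both scenarios, so it would be wrong to say that the late separation is wholly an artefact. A 10% restart rate lowers the PCT-arm curve by at most about 9 points, on one day. With equal restart rates the arm gap moves by about 2 points or less on the days worked; with 5% against 15% it can be displayed at nearly twice its true size. The primary result is not affected.

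**What to change.** - Replace the figure with the observed proportion of children on any antibiotic on each day from 0 to 14, by arm, with restarts counted as on antibiotics. State how death and discharge are handled and what the denominator is. The SAP already plans observed proportions at fixed times for children on two or more antibiotics.
- Call the text model Cox proportional hazards. Define cessation (first or final stop), and state the rules for restarts, death and discharge.
- Report hazard ratios over non-overlapping intervals, for example 0-5 and >5-14 days, in place of 0-4 and 0-10. The later ratio compares only children still on antibiotics, so it should be read as descriptive.
- Optionally, add the between-arm difference in mean days on antibiotics to day 14 with a 95% CI. This is a preference, not a correction.
- Add the protocol's reinitiation outcome to the SAP tables, so that restarts are reported somewhere.

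The cost is SAP wording, one re-specified figure and one re-specified supportive model. The figure and model use antibiotic dates already needed for the primary outcome, and reinitiation is already a protocol outcome, so no new data are required.

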#### 6.0 Study Procedures

#### Study Design

The proposed study is a prospective randomized controlled trial among children admitted to the ICU setting at Vanderbilt Children's Hospital (VCH). Enrolled subjects will receive one of two management strategies: 1) Standard of care with antimicrobial stewardship review (control), or 2) PCT testing and treatment with antimicrobial stewardship review (intervention). All subjects in both arms will have baseline audit of antimicrobial orders with feedback to providers by the antimicrobial stewardship team. For subjects in the intervention arm, the stewardship team will additionally recommend PCT testing and treatment per algorithm (Fig 1). PCT will be used in conjunction with clinical status and exam, and results of radiographic and laboratory studies, to make medical decisions about antibiotic therapy. The PCT will never be used as the sole basis for making decisions to modify or stop antibiotic therapy. The antibiotic stewardship clinicians will review all enrolled subjects (in control and intervention arms) and provide recommendations regarding antimicrobial therapy.

The ultimate decision to obtain PCT testing and/or adhere to the PCT algorithm or stewardship recommendations will be at the discretion of the ICU attending physician. Preliminary discussions with ICU faculty have revealed that they are highly supportive of the proposed study, and would be willing to adhere to the study protocol.

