- 2. Median time from randomization to first appropriate antibiotic escalation or de-escalation based on patient's clinical status and available supporting laboratory evidence, or lack thereof, of specific type of infection within 14-days post randomization.

Clinical Outcome Measures

- 1. In-hospital mortality within 30 days of randomization.
- 2. Length of stay in the hospital after randomization, up to 30 days, for those patients alive at 30 days. Length of stay will be date of discharge minus date of randomization.
- 3. Days in the ICU during hospitalization after randomization, up to 30 days, for those patients alive at 30 days.
- 4. Days spent using invasive ventilation methods (not including supplementary oxygen via nasal cannula or Vapotherm support) within 14-days post randomization.
- 5. Number of antibiotic-associated complications per patient within 14-days post randomization.
- 6. Acquisition of new hospital-acquired infections (HAIs) and/or multidrug resistant organisms (MDROs) within 30 days during index hospitalization identified on routine clinical or surveillance samples
- 7. Hospital re-admission within 30 days (yes/no)

Post Hoc Exploratory Analyses

- 1. Median DOT per patient of intravenous antibiotic therapy (in days) within 14-days post randomization
- 2. Antibiotic use > 72 hours (categorical) for any antibiotic, broad-spectrum antibiotics or IV antibiotics.
- 3. Count (%) of patients on 2 or more antibiotics at 24, 48, 72 and 96 hours after enrollment.
- 4. Total number of antibiotic stewardship recommendations made in each arm within 48-hours post randomization.

ProPICU: Statistical Analysis Plan

June 4, 2019

- 5. Rate of clinical provider compliance with adherence to suggested antibiotic escalation or de-escalation made by the antimicrobial stewardship team.
- 6. The primary endpoint will be analyzed comparing patients who:
 - Have antibiotics initiated due to concern for sepsis
 - Receive a clinical diagnosis of pneumonia
 - Have initial procalcitonin levels <0.5 ng/mL versus >0.5 ng/mL
 - Have no comorbidities versus those with comorbidities
 - Are in the pediatric intensive care unit at randomization
- 7. Number of antibiotic stewardship recommendations made in each arm within 48-hours post randomization will be analyzed (chi2 value will be compared between groups):
 - Male vs. female patients
 - Patients who receive a clinical diagnosis of pneumonia
 - Patients who have antibiotics initiated due to concern for sepsis

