Table: Days of antibiotic therapy per patient within 14 days, restricted to patients with a final diagnosis of pneumonia.

Table: Days of antibiotic therapy per patient within 14 days, restricted to patients with sepsis as their indication for antibiotics.

Table: Days of antibiotic therapy per patient within 14 days, restricted to patients with an initial procalcitonin level < 0.5 ng/mL.

Table: Days of antibiotic therapy per patient within 14 days, restricted to patients with an initial procalcitonin level > 0.5 ng/mL.

5. Antimicrobial Stewardship

Table: Number (%) of patients with a stewardship recommendation made within 48-hours of enrollment

Table: Number (%) of stewardship recommendations accepted in each arm

Table: Number (%) of recommendations to de-escalate therapy

Table: Number (%) of recommendations to escalate therapy

Table: Number (%) of recommendations to optimize dose

Table: Number (%) of recommendations to consult the infectious diseases service

Table: Number (%) of recommendations to de-label a beta-lactam allergy

ProPICU: Statistical Analysis Plan

June 4, 2019

Table: Number (%) of recommendations that were not accepted due to provider discretion

Table: Number (%) of recommendations that were not accepted due a patient medication allergy

Table: Number (%) of recommendations that were not accepted due provider waiting for 48-hour culture results

Table: Number (%) of recommendations that were not accepted due to unknown reasons

Table: Number (%) of any antibiotic change that was initiated by pediatric intensive care provider, pediatric infectious diseases provider or stewardship provider

Table: Number (%) of antibiotic escalation that was initiated by pediatric intensive care provider, pediatric infectious diseases provider or stewardship provider

Table: Number (%) of antibiotic de-escalation that was initiated by pediatric intensive care provider, pediatric infectious diseases provider or stewardship provider

6. Clinical Outcomes

Table: Number (%) of death within 30 days of randomizationMedian time from randomization to death among patients who died

Table: Median length of stay within 30 days after randomization

Table: Median length of ICU stay within 30 days after randomization

Table: Number (%) with antibiotic complication

Table: Number (%) with infection with multi-drug resistant organism

Table: Number (%) with hospital re-admission within 30 days

7. Sensitivity analysis

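### The exploratory pneumonia subgroup is defined by a diagnosis made after randomization, so its between-arm comparison is open to selection bias of unknown size and direction

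*SAP*

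**What the plan says.** Part 4 of the SAP (Sensitivity and Additional Analyses of the Primary Endpoint) lists a table of antibiotic days within 14 days "restricted to patients with a final diagnosis of pneumonia". In the SAP's Post Hoc Exploratory Analyses, items 6 and 7 describe the same group as patients who "Receive a clinical diagnosis of pneumonia". Item 6 concerns the primary endpoint and item 7 the number of stewardship recommendations. The Exploratory Objectives speak only of a diagnosis of pneumonia. None of these places gives a time point for the diagnosis or provides for adjudication blind to arm.

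The next table in part 4 handles sepsis differently: it is "restricted to patients with sepsis as their indication for antibiotics". That variable, "Indication for antibiotics", stands in SAP section 1.2 under status at entry, item g, and Pneumonia is one of its categories.

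On testing, the protocol's Laboratory Analysis section says "For subjects enrolled in the intervention arm, PCT levels will be monitored at study enrollment", with further levels over the next 2 days and at day 5. It plans a reporting comment that "Procalcitonin can help differentiate viral from bacterial respiratory infection". Under Study Design, "PCT will be used in conjunction with clinical status and exam". The Implementation section has a stewardship provider round in person to "strongly encourage provider adherence to the PCT testing and algorithm-based management".

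**The concern.** A subgroup comparison keeps the protection of the allocation only if membership is settled before the intervention can act, or cannot be influenced by it. A final diagnosis meets neither condition. In the PCT arm a low result may lead the team to settle on a viral illness without pneumonia, while a similar child in the control arm keeps the pneumonia label. The algorithm recommends de-escalation at low PCT, so the children most likely to lose the label are also likely to have short courses. The PCT arm would then keep its longer-course cases and a real reduction could be masked. If relabelling ran the other way, a benefit could appear where there is none.

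The table matters to readers. It is the first one in part 4, and protocol section 3.0 cites a paediatric pneumonia trial in which PCT guidance cut courses from 6.3 to 4.5 days, so the two results are likely to be compared. The same label defines a stewardship-recommendation subgroup in item 7.

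**Working it through.** The plan gives no pneumonia count, relabelling rate or subgroup effect, so there is no figure to reproduce. The check has two parts.

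**Passages side by side**

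- *Timing.* Final diagnosis comes after randomization; the indication for antibiotics is listed as a status at entry.
- *Exposure.* Scheduled PCT, and advice based on it, belong to the intervention arm. No blinding of the treating team is described.
- *Route.* The planned laboratory comment ties PCT to the cause of respiratory infection, so a result could plausibly influence the diagnosis.
- *Consistency.* Sepsis is defined by indication and pneumonia by final diagnosis. No reason is given for the difference.

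**Illustration of size (every input is assumed)**

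Take 100 children per arm treated for pneumonia at entry: 60 bacterial with a mean of 7 antibiotic days and 40 viral with a mean of 4. PCT has no true effect. Let r be the net share of viral children who lose the label in the PCT arm, over and above any loss in the control arm (set to 0 for simplicity).

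Control mean = 0.6 × 7 + 0.4 × 4 = 5.8 days.

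PCT-arm mean = (60 × 7 + 40(1 − r) × 4) / (60 + 40(1 − r)).

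- r = 10%: (420 + 144) / 96 = 5.875, a spurious +0.075, or about +0.08 days
- r = 25%: (420 + 120) / 90 = 6.00, +0.20 days
- r = 50%: (420 + 80) / 80 = 6.25, +0.45 days
- r = 100%: 420 / 60 = 7.00, +1.2 days

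Against the whole-trial target of 2.0 days (protocol section 10.0), these are about 4%, 10%, 23% and 60%. If the net loss of label fell in the control arm instead, the signs would reverse.

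**Effect on the planned test**

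The SAP uses a Wilcoxon rank-sum test, so a shift in means is only a guide. A simulation of 2,000 trials per scenario used other assumptions: 40 entry-pneumonia patients per arm, half bacterial (mean about 8 days) and half not (mean about 4), and no true effect. Expected differences follow the same formula, for example (0.5 × 8 + 0.5 × 0.5 × 4) / 0.75 − 6 = +0.67 at r = 50%.

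| Net relabelling in PCT arm | Spurious difference (days) | Type I error, final diagnosis | Type I error, entry indication |
|---|---|---|---|
| 0% | 0 | 4.1% | 4.1% |
| 10% | +0.11 | 5.7% | 5.8% |
| 25% | +0.29 | 7.0% | 4.8% |
| 50% | +0.67 | 15.6% | 5.4% |

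The simulation error is about 0.5 percentage points (√(0.05 × 0.95 / 2000)). At 10% relabelling no inflation can be seen; at 25% it is small; at 50% it is clear. With the entry definition the expected difference is 0 in every row.

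**The case against.** A reader might infer that the comparison *is* biased, and that it hides a true reduction. The documents do not support that. The reporting comment separates viral from bacterial infection, not pneumonia from no pneumonia, and the SAP does not restrict the subgroup to bacterial pneumonia. A child reclassified from bacterial to viral pneumonia stays in. Bias needs the further step that the pneumonia label is dropped altogether, which no passage states. The protocol also has PCT read alongside examination, imaging and other laboratory results.

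A reader might also infer that PCT can change the label in one arm only. That is true of scheduled study testing, but PCT was to be in routine clinical use and nothing bars it in controls. In the intervention arm testing is at the attending's discretion, and the SAP's last sensitivity analysis allows for PCT-arm patients with no level drawn. The arms differ in degree. Control diagnoses are revised too, on cultures, CRP and daily stewardship review, and only the net difference matters.

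Quoting 23% to 60% of the target as the likely bias would start the range at 50% net relabelling, which is extreme. Finally, the SAP lists this analysis as exploratory, so no sample-size or primary claim rests on it.

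All of this stands, and it limits the point to openness to bias in an exploratory table. It does not remove the point: membership is still set after randomization, without blinding, with more diagnostic information in one arm by design, although a baseline alternative is listed.

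**Conclusion.** The concern holds in this limited form. The pneumonia subgroup is conditioned on a label that the intervention can influence, so its between-arm comparison is open to selection bias of unknown size and direction. The illustrations run from about +0.08 days at 10% net relabelling to +1.2 days at 100%. They rest wholly on the assumed case mix, assumed course lengths and no true PCT effect, and they show what relabelling could do, not what it will do. The analysis of the primary outcome in the full modified intention-to-treat population does not use this label and is not affected. The point is worth correcting because the remedy is cheap and matches what the SAP does for sepsis.

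**What to change.** In items 6 and 7 of the Post Hoc Exploratory Analyses and in part 4 of the SAP, define the pneumonia subgroup for between-arm comparison as entry indication for antibiotics = Pneumonia (section 1.2, item g). Align the Exploratory Objectives with this. Report final diagnosis by arm descriptively. If the final-diagnosis table is kept, label it as conditioned on a post-randomization variable and draw no efficacy conclusion from it.

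The change is to SAP wording, and the variable is already listed. Two costs should be stated:

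- *Misclassification.* Some children with an entry indication of pneumonia will prove to have something else. Others with pneumonia will be missed because they were recorded under concern for sepsis, particularly if the field allows only one choice, which the SAP does not say. Neither error should depend on arm as long as the indication reflects status at entry.
- *Timing.* The SAP does not say whether the indication was recorded before the first PCT result. The SAP is dated June 4, 2019 and the protocol projects the study to end on June 30, 2019, so new wording cannot create that timing for children already enrolled. The SAP should state how and when the field was completed, and note the limitation if this cannot be established.
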